4.3 STUDY TREATMENT

The investigational medicinal product (IMP) for this study is MHAA4549A.

4.3.1 Formulation, Packaging, and Handling

4.3.1.1 MHAA4549A and Placebo

MHAA4549A will be supplied by the Sponsor in a sterile, preservative-free liquid solution in a single-use 15 mL USP/Ph. Eur. Type 1 glass vials filled to deliver 10 mL (500 mg) of MHAA4549A solution.

MHAA4549A placebo will be provided as a clear, colorless, sterile, preservative-free liquid solution and has the same vial configuration as the Drug Product.

For information on the formulation and handling of MHAA4549A, see the pharmacy manual and the Investigator's Brochure.

4.3.2 Dosage, Administration, and Compliance

4.3.2.1 MHAA4549A and Placebo

The randomization of patients will be managed by a central IxRS. All patients will be randomly assigned to receive either a single dose of MHAA4549A at 3600 mg IV, or 8400 mg IV or placebo IV at a 1:1:1 ratio.

Administration of MHAA4549A or placebo will be performed in a setting with emergency medical equipment and personnel who are trained to monitor for and respond to medical emergencies. A qualified physician *or medically qualified designee* will be on site during study drug administration for all patients. All patients will be monitored for study drug reactions during administration and for at least 30 minutes after completion of study drug administration.

A single dose of MHAA4549A or placebo will be delivered by IV infusion following dilution in 0.9% normal saline over approximately 120 minutes. Study drug should be delivered using a 0.20–0.22 µm in-line filter. Compatibility testing has shown that MHAA4549A is stable when diluted in 0.9% normal saline in a polyvinylchloride, polyolefin bag, or ethylene vinyl acetate bag (EVA), at or above a combined total concentration of 0.24 mg/mL up to 27.0 mg/mL. Study drug must be administered within the treatment window outlined in Section 3.1.1. Further detailed instructions can be found in the Pharmacy Manual.

Subjects who experience a moderate-to-severe infusion related reaction should have their infusion stopped. The infusion should not be restarted. The infusion will be discontinued in the event that the subject experiences a serious reaction and further dosing of subjects halted until safety of the drug is assessed.

There are no recommended dosage modifications for MHAA4549A because it is a single infusion. Any overdose or incorrect administration of study drug should be noted on the

Study Drug Administration electronic Case Report Form (eCRF). Adverse events associated with an overdose or incorrect administration of study drug should be recorded on the Adverse Event eCRF. General supportive measures will be taken to manage any adverse events associated with overdose. Patients experiencing such adverse events will be followed up clinically until the event has resolved.

Trained clinical site staff responsible for adequate and accurate study drug administration, accounting, and management will administer study drugs to patients. Study drug preparation and dosing instructions will be provided to each site. The exact times of study drug administration will be recorded in the relevant dispensing/administration logs and patient's source notes. Any noncompliance or problems with study drug administration will be recorded in the patient's source notes and reported to the Sponsor if appropriate.

4.3.3 Investigational Medicinal Product Accountability

IMPs required for completion of this study (MHAA4549A) will be provided by the Sponsor. The study site will acknowledge receipt of IMPs and confirm the shipment condition and content. Any damaged shipments will be replaced.

The IMP will be stored in a secure pharmacy or locked area, with access limited to authorized personnel, in accordance with the details provided in the Investigator's Brochure and Pharmacy Manual. Upon receipt, MHAA4549A and placebo vials must be refrigerated at 2°C–8°C until use. MHAA4549A does not contain antimicrobial preservatives; therefore, care must be taken to ensure that the solution for infusion is not microbiologically compromised during preparation. Dilute under appropriate aseptic conditions using 0.9% normal saline. The solution for infusion should be used immediately. If not used immediately, in-use storage times and conditions prior to use should not exceed 24 hours at 2°C–8°C and/or 4 hours at ambient temperature (18°C–24°C). If the dose solution is stored at 2°C–8°C, it should be removed from refrigeration and allowed to reach room temperature prior to administration. If the infusion is interrupted and the combined ambient temperature storage and interruption time exceeds 4 hours, prepare a new dose solution to resume the infusion (see the Pharmacy Manual). Protect dose solutions from heat and intense light. Vials are intended for single use only; therefore, any remaining solution should be discarded.

IMPs will either be disposed of at the study site according to the study site's institutional standard operating procedure or returned to the Sponsor with the appropriate documentation. The site's method of IMP destruction must be agreed to by the Sponsor. The site must obtain written authorization from the Sponsor before any IMP is destroyed, and IMP destruction must be documented on the appropriate form.

Accurate records of all IMPs received at, dispensed from, returned to, and disposed of by the study site should be recorded on the Drug Inventory Log.

4.3.4 Post-Trial Access to MHAA4549A

As this is single dose administration, the Sponsor does not intend to provide MHAA4549A to patients after the conclusion of the study or any earlier withdrawal. Patients may or may not be eligible for any potential subsequent trials of MHAA4549A under a separate protocol.

The Roche Global Policy on Continued Access to Investigational Medicinal Product is available at the following Web site:

http://www.roche.com/policy_continued_access_to_investigational_medicines.pdf

4.4 CONCOMITANT THERAPY AND FOOD

Concomitant therapy includes any medication (e.g., prescription drugs, over-the-counter drugs, herbal or homeopathic remedies, nutritional supplements) used by a patient from 30 days prior to screening to the study completion/discontinuation visit. All such medications should be reported to the investigator and recorded on the Concomitant Medications eCRF.

4.4.1 Permitted Therapy

Patients who use oral contraceptives, hormone-replacement therapy, or other maintenance therapy should continue their use.

Acetaminophen/paracetamol and non-steroidal anti-inflammatory drugs (NSAIDs) are allowed for relief of severe influenza symptoms. The patient must record the use of these medications as directed in the patient diary.

Patients with recurrent influenza infection may be given local standard of care anti-influenza treatments including neuraminidase inhibitors.

4.4.2 Prohibited Therapy

Use of the following therapies is prohibited throughout the patient's participation in the study (from enrollment to end of study):

- Any influenza antiviral therapy (e.g., oseltamivir, zanamivir, peramivir, amantadine, rimantadine) from onset of influenza-like illness (*except for recurrent influenza as described in Section 3.1.1*)
- Investigational therapy
- Oral/inhaled corticosteroids
- Antitussives or expectorants
- Combination cold or influenza remedies
- Antihistamines
- Herbal medicines for influenza virus infection

4.4.3 Prohibited Food

There are no prohibited foods for this study.

4.5 STUDY ASSESSMENTS

Please see [Appendix 1](#) for the schedule of *activities* performed during the study.

4.5.1 Informed Consent Forms and Screening Log

Written informed consent for participation in the study must be obtained before performing any *study-related procedures*. Informed Consent Forms for enrolled patients and for patients who are not subsequently enrolled will be maintained at the study site.

All screening evaluations must be completed and reviewed to confirm that patients meet all eligibility criteria before randomization. The investigator will maintain a screening log to record details of all patients screened and to confirm eligibility or record reasons for screening failure, as applicable.

4.5.2 Diagnostic Testing for Enrollment

All patients must be assessed for influenza A disease confirmation prior to enrollment into the study. A rapid PCR test or rapid antigen test is required for diagnosis of influenza A infection. For the diagnostic test, sample collection may involve a nasal swab or a nasopharyngeal swab, depending on the diagnostic platform at the site.

4.5.3 Medical History and Demographic Data

Medical history includes clinically significant diseases and procedures, including chronic respiratory disease, infections, surgeries, cancer history (including prior cancer therapies and procedures), reproductive status, smoking history, use of alcohol and drugs of abuse, and all medications (e.g., prescription drugs, over-the-counter drugs, herbal or homeopathic remedies, nutritional supplements) used by the patient within 30 days prior to the screening visit.

Demographic data will include age, sex, and self-reported race/ethnicity.

4.5.4

[REDACTED]

4.5.5 Physical Examinations

A complete physical examination *should be performed at screening and* should include an evaluation of the head, eyes, ears, nose, and throat, and the cardiovascular, dermatological, musculoskeletal, respiratory, gastrointestinal, genitourinary, and neurological systems. Any abnormality identified at baseline should be recorded on the General Medical History and Baseline Conditions eCRF.

At subsequent visits (or as clinically indicated), limited, symptom-directed physical examinations should be performed. Changes from baseline abnormalities should be recorded in patient notes. New or worsened clinically significant abnormalities should be recorded as adverse events on the Adverse Event eCRF.

4.5.6 Vital Signs

Vital signs will include measurements of respiratory rate, pulse rate, temperature (*oral*), and systolic and diastolic blood pressures while the patient is in a seated or supine position for at least 5 minutes.

4.5.7 Laboratory, Biomarker, and Other Biological Samples

Samples for the following laboratory tests will be sent to the study site's local laboratory for analysis:

Table 2 Laboratory, Biomarker, and Other Biological Samples

Hematology: Hemoglobin Hematocrit Red blood cell (RBC) count Platelet count WBC absolute and differential: Total neutrophils (bands & segments, if clinically indicated) Lymphocytes Monocytes Eosinophils Basophils Coagulation: Prothrombin time (PT) Activated partial thromboplastin time (aPTT) Urinalysis: pH Specific gravity Glucose Protein Ketones Blood Bilirubin Nitrite Leukocyte esterase Microscopic examination (if clinically indicated)
	
Clinical Chemistry: Glucose Blood urea nitrogen (BUN) or urea Creatinine Total protein Albumin Total bilirubin Alkaline phosphatase (ALP) Aspartate aminotransferase (AST) Alanine aminotransferase (ALT) Triglycerides Amylase (lipase will be reflexively assessed on all samples with amylase > ULN) Calcium Phosphorus Sodium Potassium Chloride Bicarbonate Lactate dehydrogenase (LDH) Gamma glutamyl transferase (GGT) Misc: Pregnancy test (urine or serum; women of child-bearing potential; at screening only)

--	--

The following samples will be sent to the Sponsor or a designee for analysis:

- [REDACTED]
- [REDACTED]
- [REDACTED]
- [REDACTED]
- [REDACTED]

For sampling procedures, storage conditions, and shipment instructions, see the laboratory manual.

4.5.8 Electrocardiograms

Single ECG recordings will be obtained at specified timepoints, as outlined in the schedule of *activities* (see [Appendix 1](#)), and may be obtained at unscheduled timepoints as indicated.

All ECG recordings must be performed using a standard high-quality, high-fidelity digital electrocardiograph machine equipped with computer-based interval measurements. Lead placement should be as consistent as possible. ECG recordings must be performed after the patient has been resting in a supine position for at least 10 minutes. All ECGs are to be obtained prior to other procedures scheduled at that same time (e.g., vital sign measurements, blood draws) and *if possible*, should not be obtained within 3 hours after any meal. Circumstances that may induce changes in heart rate, including environmental distractions (e.g., television, radio, conversation) should be avoided during the pre-ECG resting period and during ECG recording.

For safety monitoring purposes, the investigator must review, sign, and date all ECG tracings. Paper copies of ECG tracings will be kept as part of the patient's permanent study file at the site. The following should be recorded in the appropriate eCRF: heart rate, RR interval, QRS interval, PR duration, uncorrected QT interval, and QT interval corrected using Fridericia's formula (QTcF) (*or Bazett's formula [QTcB] if QTcF is not available*) based on the machine readings of the individual ECG tracings. Any morphologic waveform changes or other ECG abnormalities must be documented on the eCRF. If considered appropriate by the Sponsor, ECGs may be analyzed retrospectively at a central laboratory.

If at a particular postdose timepoint the mean corrected QT interval is >500 ms and/or >60 ms longer than the baseline value, another ECG must be recorded, ideally within the next 5 minutes, and ECG monitoring should continue until the corrected QT interval has stabilized on two successive ECGs. The Medical Monitor should be notified. Standard-of-care treatment may be instituted per the discretion of the investigator. If a PK sample is not scheduled for that timepoint, an unscheduled PK sample should be obtained. A decision on study drug discontinuation should be made, as described in Section 3.1.4. The investigator should also evaluate the patient for potential concurrent risk factors (e.g., electrolyte abnormalities, co-medications known to prolong the QT interval, severe bradycardia).

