3.1.4 Stopping Rules

Further dosing in a treatment arm or in the entire study will be suspended if any of the following criteria is met:

- *If any patient experiences a life-threatening adverse event related to MHAA4549A*
- *If a single serious adverse event is deemed related to MHAA4549A*
- *If a patient experiences a persistent post-dose corrected QT interval >500 ms and/or >60 ms longer than the baseline value related to MHAA4549A*

- *If ≥ 2 patients out of all patients who have received MHAA4549A to date (including this or any other study) experience similar adverse events that meet causality criteria (see Section 5.3.4):*

An unexpected worsening of influenza inconsistent with the usual course of disease

Any intolerable systemic reaction that results in a significant compromise in the ability to conduct activities of daily living

A suspected systemic immunological reaction to study drug

If a patient *in the blinded study* experiences any of the above (i.e., conditions of sufficient severity that risk would exceed benefit), the Investigator must *immediately* notify the Sponsor, *who will suspend all dosing in the study and convene a meeting of the SMC* within 24 hours *following* knowledge of the event. If, after a review of the blinded study data, the SMC unanimously agrees with the Investigator's original assessment that the event *would meet Stopping Criteria if the patient had received active drug, the patient's treatment will be unblinded to the SMC.* If the patient *did* receive MHAA4549A, *further dosing within the entire study must be suspended until the SMC consults with the IMC and SOC.*

In addition to the above criteria, dosing will also be halted if the IMC and SOC conclude there is a clinically significant imbalance in toxicity between one or both of the arms receiving MHAA4549A and the arm receiving placebo

Dosing may only resume if the IMC and SOC, *in consultation with the SMC,* unanimously determine *that Stopping Criteria have not been met for at least one (or for both) of the dose levels in this study. Any decision on whether Stopping Criteria have been met will always be made following a review of all unblinded data from this and any previous study that examined MHAA4549A.*

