6.3 SUMMARIES OF TREATMENT GROUP COMPARABILITY

Demographic and baseline characteristics of the patient will be summarized for all randomized patients by treatment group by use of descriptive statistics. Baseline is defined as the last available value prior to study drug administration. During the study patient disposition, concurrent treatment, and compliance with study treatment and visits will be summarized on the safety analysis population using descriptive statistics.

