Appendix 1 Schedule of Activities

	Screening (-72 hours to 0 hours)	D1 ^a (Randomization)	D2	D3	D4	D5	D6	D7 (±1)	D8- 13	D14 (±2)	D30 (±7)	D100 (±7)	Unscheduled Visit	Early Discontinuation
Informed consent ^b	x													Complete all assessments for the current day. If a patient discontinues early after Day 7, only a telephone visit is required as the Early Discontinuation visit.
Rapid PCR test or rapid antigen test ^c	x													
Inclusion/exclusion criteria	x													
Medical history and demographics	x													
Seasonal influenza vaccine history	x													
Confirm onset flu symptoms	x													
Pregnancy screening ^d	x													
Concomitant medications ^e	x	x	x	x	x	x	x	x	x	x	x	x	x	
Vital signs ^f	x	x		x				x					x	
Electrocardiogram (12-lead) ^g	x	x ^h		x				x					(x)	
MHAA4549A/Placebo administration ⁱ		x												
Complete physical examination ^j	x												(x)	
Limited, symptom-directed physical examination/symptom assessment ^k		x		x				x					x	
Weight and height ^l	x	x		x				x					(x)	
Adverse events		x	x	x	x	x	x	x	x	x	x	x	x	
Hematology ^m	x			x				x					(x)	
Chemistry panel ^m	x			x				x					(x)	
Coagulation panel ^m		x												
Urinalysis ⁿ	x			x				x					(x)	
██████████ ██████████		x		x		x		x					(x)	

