Appendix 1 (cont'd) Schedule of *Activities*

- ^f Vital signs will be collected within 1 hour before MHAA4549A infusion and within 1 hour after completion of MHAA4549A infusion and include temperature (*oral*), respiratory rate, heart rate, systolic blood pressure, and diastolic blood pressure. Temperature should be measured using the same methodology throughout the study and should be measured prior to administration of any antipyretic drugs. Temperature, blood pressure, respiratory rate, and heart rate will be completed after the patient has been in a seated or supine position for at least 5 minutes.
- ^g Patient should rest in a supine position for 10 minutes prior. If screening ECG is taken within 1-3 hours pre-dose, Day 1 pre-dose ECG does not need to be taken.
- ^h On Day 1, ECG must be taken within 1-3 hours pre-dose and 1-3 hours post-dose.
- ⁱ All patients will be monitored for study drug reactions during administration and for at least 30 minutes after completion of study drug administration.
- ^j Complete physical examination includes evaluations of general appearance of head, eye, ear, nose, and throat, cardiovascular, dermatological, musculoskeletal, respiratory, gastrointestinal, genitourinary, and neurological systems. Changes from any prior examination should be recorded. New or worsened abnormalities should be recorded as AEs, if appropriate.
- ^k Limited, symptom-directed physical examination includes, at a minimum, evaluation of general appearance, dermatological examination of the injection sites, evaluations directed by patient-reported symptoms, and any other evaluations that the investigator deems clinically relevant. Changes from any prior examination should be recorded. New or worsened abnormalities should be recorded as AEs.
- ^l Height will be obtained at screening only. Weight will be obtained at all indicated visits (pre-infusion on Day 1). Height and weight will be recorded in centimeters and kilograms, respectively
- ^m Local laboratory measurements should be utilized. Hematology *and* chemistry panel at screening must be collected within 36 hours prior to study drug administration. Lipase will be reflexively assessed on all samples with amylase >ULN.

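### The Bazett fallback in section 4.5.8 can understate a QTc rise against the >60 ms limit when heart rate falls after an acute-illness baseline, and it is unnecessary because QT and RR are both recorded

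*Combined protocol and SAP*

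**What the plan says.** Section 4.5.8 calls for single ECGs and has the site enter "heart rate, RR interval, QRS interval, PR duration, uncorrected QT interval" in the eCRF, together with QTcF or Bazett's "formula [QTcB] if QTcF is not available". The corrected value is taken from the printout, "based on the machine readings of the individual ECG tracings". Central reading is optional and retrospective.

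Two rules act on the corrected value:

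- **Repeat-ECG trigger (4.5.8):** "If at a particular postdose timepoint the mean corrected QT interval is >500 ms and/or >60 ms longer than the baseline value", a further ECG is required, the Medical Monitor is notified, and an unscheduled PK sample is drawn if none is due.
- **Stopping rule (3.1.4):** dosing is suspended for a "persistent post-dose corrected QT interval >500 ms and/or >60 ms longer than the baseline value related to MHAA4549A".

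Neither rule names Fridericia or Bazett, and neither requires the same formula at both timepoints. Section 6.4 lists ECGs among the safety parameters without naming a formula.

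Section 6.3 states: "Baseline is defined as the last available value prior to study drug administration". Under section 4.1.1, dosing starts within 72 hours of illness onset in patients with moderate or severe symptoms, fever being one listed example. Appendix 1 says "On Day 1, ECG must be taken within 1-3 hours pre-dose and 1-3 hours post-dose", with further scheduled ECGs on Days 3 and 7.

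**The concern.** A change limit works only if the quantity on both sides of the subtraction means the same thing. QTcB carries a heart-rate term that QTcF does not, so a change in QTcB mixes any drug effect on repolarisation with the change in heart rate. Here the baseline is taken in acute illness and two of the post-dose ECGs fall on Days 3 and 7, when recovery could have slowed the heart. In that case the Bazett change is too small. If heart rate rises instead, it is too large and gives a false alarm. If one formula is used at baseline and the other after dosing, the error can go either way and can be larger.

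The trigger operates in real time. A missed alert means no repeat ECG, no Medical Monitor notification and no unscheduled PK sample, and a persistent, drug-related prolongation might not reach the stopping rule. Recalculating QTcF at analysis repairs the summary tables but not the missed alert. A false alarm also has a cost: section 3.1.4 has the Sponsor suspend all dosing and convene the Safety Monitoring Committee once an investigator reports a qualifying event.

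**Working it through.** The plan gives no figure to reproduce: 500 ms and 60 ms are set limits. The check applies the two correction formulas to those limits.

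**Inputs from the protocol.** Limits of >500 ms and >60 ms (3.1.4, 4.5.8); QT and RR recorded on every tracing (4.5.8); baseline is the last pre-dose value (6.3); post-dose ECGs on Days 1, 3 and 7 (Appendix 1).

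**Assumptions, because the documents give no values.** Baseline QTcF 405 ms (390 and 420 as sensitivity); heart rate 90–120 bpm at baseline and 70–80 bpm on Day 3 or 7.

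**Formulas.** With RR = 60/HR in seconds, QTcF = QT/RR^(1/3) and QTcB = QT/RR^(1/2). Dividing gives QTcB = QTcF × (HR/60)^(1/6). The multiplier is 1.0260 at 70 bpm, 1.0491 at 80, 1.0699 at 90, 1.0889 at 100, 1.1063 at 110 and 1.1225 at 120.

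**Step 1: what a 61 ms QTcF rise reads as in QTcB (405 to 466 ms).** Example, 100 to 70 bpm: baseline QTcB = 405 × 1.0889 = 441.0; post-dose QTcB = 466 × 1.0260 = 478.1; change = 37.1 ms.

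**Step 2: QTcF rise needed for a QTcB change of 60 ms.** (baseline QTcB + 60) / post-dose multiplier − 405. For 100 to 70 bpm: 501.0/1.0260 − 405 = 83.3 ms.

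**Step 3: QTcF rise at which QTcB reaches 500 ms.** 500/1.0260 = 487.3, a rise of 82.3 ms, at 70 bpm; 500/1.0491 = 476.6, a rise of 71.6 ms, at 80 bpm.

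| Heart rate (bpm) | 61 ms QTcF rise reads as QTcB (ms) | QTcF rise needed, 60 ms limb alone (ms) | QTcF rise needed, either limb (ms) |
|---|---|---|---|
| 90 to 80 | 55.6 | 65.2 | 65.2 |
| 90 to 70 | 44.8 | 75.8 | 75.8 |
| 100 to 80 | 47.9 | 72.5 | 71.6 |
| 100 to 70 | 37.1 | 83.3 | 82.3 |
| 110 to 70 | 30.1 | 90.2 | 82.3 |
| 120 to 70 | 23.5 | 96.5 | 82.3 |

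**Step 4: other baselines, either limb.** At 390 ms the first rise that fires is 64.9–95.1 ms. At 420 ms it is 67.3 ms at 70 bpm. At 420 ms and 80 bpm the 500 ms limb fires at 56.6 ms, so nothing above 60 ms is missed.

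**Step 5: heart rate rising, 80 to 100 bpm, baseline 405 ms.** With no QTcF change, QTcB reads 405 × (1.0889 − 1.0491) = +16.1 ms, and a QTcF rise of 40.3 ms already reads as 60 ms.

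**Step 6: mixed formulas, baseline 405 ms.**
- QTcF at baseline, QTcB after dosing: a QTcF rise of 38.2 ms (80 bpm), 29.6 ms (90) or 22.0 ms (100) reads as 60 ms.
- QTcB at baseline, QTcF after dosing: a 61 ms rise reads as 32.7 ms (baseline 90 bpm), 25.0 ms (100) or 17.9 ms (110).

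**The case against.** The strongest reply is that several conditions must coincide: a machine that prints no QTcF although section 4.5.8 asks for high-quality digital equipment, a clear fall in resting heart rate after 10 minutes supine, and a true rise inside a limited window. The protocol shows none of these. The highest assumed rates count as tachycardia on the scale in Appendix 3. The >500 ms limb becomes more sensitive under Bazett above 60 bpm and closes part of the gap. At baseline 405 ms, a missed tracing would still print a QTcB of about 478–500 ms for an investigator who must review and sign it, and the safety committees also review the data. Each patient has a single infusion, so a Day 3 or Day 7 alert cannot alter that patient's dose. The Day 1 post-dose ECG is hours from its baseline and less exposed. Completed studies reported no ECG safety issue. Mixing formulas would also need a patient's machines to differ between visits.

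Most of this stands as a limit on frequency and consequence, and it is why the point is a recommended change and not an essential one. It does not rescue the wording. Nothing elsewhere names the formula for the trigger, central reading comes too late for an alert, and a site that follows the fallback exactly can get the wrong answer to the >60 ms question. The objection is also right that an eCRF-derived field may be filled too late for a real-time alert, and the fix below allows for that.

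**Conclusion.** The concern holds. Where the fallback is used and heart rate falls from baseline, the >60 ms limb understates the QTcF rise. At a baseline QTcF of 405 ms and a fall from 90–120 to 70–80 bpm, a 61 ms rise reads as 24–56 ms. With both limbs counted, QTcF rises above 60 ms and up to 65–82 ms are missed. The upper end is 65–95 ms at a baseline of 390 ms. At 420 ms it is 67 ms at 70 bpm, with nothing missed at 80 bpm. A rising heart rate produces false alarms instead.

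The heart rates and baseline values are assumptions, and the frequency of fallback use is unknown and could be near zero. The >500 ms limb is not masked above 60 bpm. No bias between arms is claimed, and the ECG summaries can be recovered from the stored QT and RR. What is affected is the real-time safety trigger. The change is worth making because the stated reason for the fallback, that QTcF is unavailable, does not apply when QT and RR are recorded on the same form.

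**What to change.** - In 4.5.8, delete the Bazett alternative. Require QTcF = QT/RR^(1/3), RR in seconds, from the recorded QT and RR on every baseline and post-dose tracing.
- Where the machine does not print QTcF, have the site calculate it when the tracing is reviewed, so that it is ready for the alert. An eCRF-derived field can serve as the record and a cross-check.
- Name QTcF in the 4.5.8 trigger and in the 3.1.4 stopping rule, and use it in the ECG summaries.
- Remove the word mean from the 4.5.8 trigger, since single ECGs are taken.
- Leave the 500 ms and 60 ms limits as they are.

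The cost is one sentence in 4.5.8, one word in 3.1.4 and a derived eCRF field, with no new measurements. The downside is a short calculation, with some risk of arithmetic error, at sites whose machines do not print QTcF. If such machines are rare, so is the burden.
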